14.3.2 Safety Analyses

All safety data will be populated in the individual CRFs. All safety data will be listed by subjects.

Dosing dates and times will be listed by subject.

AEs will be coded using the Medical Dictionary for Regulatory Activities (MedDRA[®]) and summarized by treatment for the number of subjects reporting the treatment emergent adverse event (TEAE) and the number of TEAEs reported. A by-subject AE data listing including verbatim term, coded term, treatment, severity, and relationship to treatment will be provided.

Safety data including ECGs, physical examinations, vital signs assessments, clinical laboratory results, will be summarized by treatment and point of time of collection.

Descriptive statistics using appropriate summary statistics will be calculated for quantitative safety data as well as for the difference to baseline, when appropriate.

Concomitant medications will be listed by subject and coded using the WHO drug dictionary. Medical history will be listed by subject.

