### 3. STUDY DESIGN

This is an open label, randomized, 4-treatment, crossover study.

CCI [REDACTED] healthy, adult male and female subjects (women of non-childbearing potential only) were enrolled. Every attempt were made to enroll at least 3 subjects of each sex in the study.

Screening of subjects occurred within 28 days prior to the first dosing.

Subjects were randomized to one of four treatment sequences: ABCD, ABDC, BACD, and BADC. Every attempt was made to include the same number of females in each sequence and the same number of males in each sequence.

On Day 1 of Periods 1 and 2, a single oral dose of LOXO-292 was administered under fasted or fed conditions, according to the randomization schedule, followed by PK sampling for 168 hours.

In Periods 3 and 4, multiple oral doses of omeprazole were administered once daily from Day -4 of Period 3 until Day 7 of Period 4, inclusive (for a total of 18 consecutive days) with a single oral dose of LOXO-292 coadministered on Day 1 of each period under fasted or fed conditions, according to the randomization schedule. Pharmacokinetic sampling for LOXO-292 was taken for 168 hours following LOXO-292 dosing on Day 1 in each period.

There was a washout period of 7 days between LOXO-292 dose in Period 1 and LOXO-292 dose in Period 2 and between the LOXO-292 dose in Period 2 and the first dose of omeprazole in Period 3. There was no washout between Periods 3 and 4 omeprazole doses although the LOXO-292 doses will be separated by a 7-day washout.

Safety was monitored throughout the study by repeated clinical and laboratory evaluations.

Subjects were permitted to be replaced at the discretion of the Sponsor, but no subjects were replaced on this study.

Subjects were housed throughout the study beginning on Day -1 of Period 1, at the time indicated by the CRU, until after completion of the 168-hour blood draw and/or study procedures in Period 4. At all times, a subject may have been required to remain at the CRU for longer at the discretion of the Principal Investigator (PI) or designee.

The CRU made every attempt to contact all subjects who received at least 1 dose of study drug (including subjects who terminated the study early) using their standard procedures (i.e., phone call or other method of contact) approximately 7 days after the

last study drug administration (LOXO-292 or omeprazole, whichever came last) to determine if any AE had occurred since the last study visit.

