**Table 7.5 Vital Signs Time Points**

Period	Period Day	Study Hour	Parameter
Screen	Screening		HR, BP, RR, T
1	Day -1	0*	HR, BP, RR
1	Day 1	2	HR, BP, RR
1	Day 4	72	HR, BP, RR
2	Day 1	0**	HR, BP, RR
2	Day 1	2	HR, BP, RR
2	Day 4	72	HR, BP, RR
3	Day 1	0**	HR, BP, RR
3	Day 1	2	HR, BP, RR
3	Day 4	72	HR, BP, RR
4	Day 1	0**	HR, BP, RR
4	Day 1	2	HR, BP, RR
4	Day 4	72	HR, BP, RR
4	Day 8	168***	HR, BP, RR, T

\* performed within 24 hours prior dosing  
\*\* performed prior dosing  
\*\*\* performed at the end of Period 4 or prior to ET

Descriptive statistics will be reported for vital sign measurements (blood pressure, pulse, and respiration rate) and change from baseline by treatment and time point. Baseline is Day -1 of Period 1 and Day 1 predose of Period 2, 3, 4 and is the last non-missing predose measurement prior to dosing of LOXO-292, including rechecks and unscheduled assessments. Postdose recheck values and ET results will not be used for calculation of descriptive statistics. All vital signs results will be listed by subject.

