**Table 7.6: ECG Time Points**

Period	Period Day	Study Hour
Screen	Screening	
1	Day -1	0*
1	Day 1	2
1	Day 4	72
2	Day 1	0**
2	Day 1	2
2	Day 4	72
3	Day 1	0**
3	Day 1	2
3	Day 4	72
4	Day 1	0**
4	Day 1	2
4	Day 4	72
4	Day 8	168***

\* performed within 24 hours prior dosing  
\*\* performed prior dosing  
\*\*\* performed at the end of Period 4 or prior to ET

Descriptive statistics will be reported for ECG parameters and change from baseline by treatment and time point. Baseline is Day -1 of Period 1 and Day 1 predose of Period 2, 3, 4 and is the last non-missing predose measurement prior to dosing of LOXO-292, including rechecks and unscheduled assessments. Postdose recheck values and ET results will not be used for calculation of descriptive statistics. QTcF values that are > 450 msec and increase from baseline > 30 msec will be flagged in the data listing. All ECG interval parameters will be listed by subject and time point of collection.

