Prior to Treatment C or D at Period 3, subjects were administered with multiple daily doses of 40 mg omeprazole (1 x 40 mg capsule) from Day -4 to Day -1 of Period 3.

Program: /CAXXXXX/sas\_prg/stsas/tab\_programname.sas DDMMYYYY HH:MM

Table 14.3.5.7 Vital Sign Summary and Change from Baseline (Safety Population)

Vital Sign Parameter (unit)	Time Point	Statistic	Treatment				Change From Baseline			
			A	B	C	D	A	B	C	D
Parameter1 (unit)	Day -1/1\$	n	XX	XX	XX	XX				
		Mean	XX.XX	XX.XX	XX.XX	XX.XX				
		SD	X.XXX	X.XXX	X.XXX	X.XXX				
		Minimum	XX.X	XX.X	XX.X	XX.X				
		Median	XX.XX	XX.XX	XX.XX	XX.XX				
		Maximum	XX.X	XX.X	XX.X	XX.X				
	Postdose Hour 2	n	XX	XX	XX	XX	XX	XX	XX	XX
		Mean	XX.XX	XX.XX	XX.XX	XX.XX	XX.XX	XX.XX	XX.XX	XX.XX
		SD	X.XXX	X.XXX	X.XXX	X.XXX	X.XXX	X.XXX	X.XXX	X.XXX
		Minimum	XX.X	XX.X	XX.X	XX.X	XX.X	XX.X	XX.X	XX.X
		Median	XX.XX	XX.XX	XX.XX	XX.XX	XX.XX	XX.XX	XX.XX	XX.XX
		Maximum	XX.X	XX.X	XX.X	XX.X	XX.X	XX.X	XX.X	XX.X
	Postdose Hour 72	n	XX	XX	XX	XX	XX	XX	XX	XX
		Mean	XX.XX	XX.XX	XX.XX	XX.XX	XX.XX	XX.XX	XX.XX	XX.XX
		SD	X.XXX	X.XXX	X.XXX	X.XXX	X.XXX	X.XXX	X.XXX	X.XXX
		Minimum	XX.X	XX.X	XX.X	XX.X	XX.X	XX.X	XX.X	XX.X
		Median	XX.XX	XX.XX	XX.XX	XX.XX	XX.XX	XX.XX	XX.XX	XX.XX
		Maximum	XX.X	XX.X	XX.X	XX.X	XX.X	XX.X	XX.X	XX.X

<Programmer note: Similar for remaining vital sign parameters. Treatment D has an additional time point: Postdose Hour 168.>

Note: \$ Day -1 for Period 1 and Day 1 for Period 2, 3, 4

Baseline is Day -1 of Period 1 and Day 1 predose of Period 2, 3, 4 and is the last non-missing predose measurement prior to dosing of LOXO-292, including rechecks and unscheduled assessments.

Treatment A: <description>

Treatment B: <description>

Treatment C: <description>

Treatment D: <description>

Prior to Treatment C or D at Period 3, subjects were administered with multiple daily doses of 40 mg omeprazole (1 x 40 mg capsule) from Day -4 to Day -1 of Period 3.

Program: /CAXXXX/sas\_prg/stsas/tab\_PROGRAMNAME.sas DDMMMYYYY HH:MM

Table 14.3.5.8 12-Lead Electrocardiogram Summary and Change from Baseline (Safety Population)

ECG Parameter (unit)	Time Point	Statistic	Treatment				Change From Baseline			
			A	B	C	D	A	B	C	D
Parameter1 (unit)	Day -1/1\$	n	XX	XX	XX	XX				
		Mean	XX.XX	XX.XX	XX.XX	XX.XX				
		SD	X.XXX	X.XXX	X.XXX	X.XXX				
		Minimum	XX.X	XX.X	XX.X	XX.X				
		Median	XX.XX	XX.XX	XX.XX	XX.XX				
		Maximum	XX.X	XX.X	XX.X	XX.X				
	Postdose Hour 2	n	XX	XX	XX	XX	XX	XX	XX	XX
		Mean	XX.XX	XX.XX	XX.XX	XX.XX	XX.XX	XX.XX	XX.XX	XX.XX

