		SD	X.XXX	X.XXX	X.XXX	X.XXX	X.XXX	X.XXX	X.XXX	X.XXX
		Minimum	XX.X	XX.X	XX.X	XX.X	XX.X	XX.X	XX.X	XX.X
		Median	XX.XX	XX.XX	XX.XX	XX.XX	XX.XX	XX.XX	XX.XX	XX.XX
		Maximum	XX.X	XX.X	XX.X	XX.X	XX.X	XX.X	XX.X	XX.X
	Postdose Hour 72	n	XX	XX	XX	XX	XX	XX	XX	XX
		Mean	XX.XX	XX.XX	XX.XX	XX.XX	XX.XX	XX.XX	XX.XX	XX.XX
		SD	X.XXX	X.XXX	X.XXX	X.XXX	X.XXX	X.XXX	X.XXX	X.XXX
		Minimum	XX.X	XX.X	XX.X	XX.X	XX.X	XX.X	XX.X	XX.X
		Median	XX.XX	XX.XX	XX.XX	XX.XX	XX.XX	XX.XX	XX.XX	XX.XX
		Maximum	XX.X	XX.X	XX.X	XX.X	XX.X	XX.X	XX.X	XX.X

<Programmer note: Similar for remaining ECG parameters. Treatment D has an additional time point: Postdose Hour 168.>

Note: \$ Day -1 for Period 1 and Day 1 for Period 2, 3, 4

Baseline is Day -1 of Period 1 and Day 1 predose of Period 2, 3, 4 and is the last non-missing predose measurement prior to dosing of LOXO-292, including rechecks and unscheduled assessments.

Treatment A: <description>

Treatment B: <description>

Treatment C: <description>

Treatment D: <description>

Prior to Treatment C or D at Period 3, subjects were administered with multiple daily doses of 40 mg omeprazole (1 x 40 mg capsule) from Day -4 to Day -1 of Period 3.

Program: /CAXXXX/sas\_prg/stsas/tab\_PROGRAMNAME.sas DDMMYYYY HH:MM

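### Two SAP table shells give the Hour 168 vital signs and ECG to Treatment D only, although Period 4 is Treatment C in two of the four sequences

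*SAP*

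**What the plan says.** SAP Section 3 gives the design: "Subjects were randomized to one of four treatment sequences: ABCD, ABDC, BACD, and BADC". Protocol Section 12.3 lists the same four sequences. SAP Section 5 places Treatments C and D in Periods 3 and 4, in randomized order.

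SAP Table 7.5 (vital signs) and Table 7.6 (ECG) each contain one Hour 168 row, at Period 4 Day 8. Its footnote reads "performed at the end of Period 4 or prior to ET". The row is defined by period and names no treatment.

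For the ECG, SAP Section 7.6 states: "Descriptive statistics will be reported for ECG parameters and change from baseline by treatment and time point". Section 7.5 has the same rule for blood pressure, pulse and respiration rate. Protocol Section 14.3.2 says that safety data, including ECGs and vital signs, "will be summarized by treatment and point of time of collection". None of these texts restricts Hour 168 to one treatment.

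The shells do. The programmer note to Table 14.3.5.7 says "Treatment D has an additional time point: Postdose Hour 168", and the note to Table 14.3.5.8 says "Similar for remaining ECG parameters. Treatment D has an additional time point: Postdose Hour 168". Neither mentions Treatment C or Period 4.

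**The concern.** The notes would be right only if every subject received Treatment D last. The design deliberately randomizes the order of C and D, so in half of the sequences the end-of-study assessment follows Treatment C. A programmer who builds the tables from the notes would leave the Treatment C column without an Hour 168 row, and the scheduled end-of-study vital signs and ECGs of those subjects would not be summarised anywhere.

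Safety and tolerability of LOXO-292 with and without food and omeprazole is the secondary objective, and vital signs and ECGs are named safety endpoints. Hour 168 is the last scheduled measurement of both. The tables would show it for omeprazole with LOXO-292 fed (D) and not for omeprazole with LOXO-292 fasted (C). A reader of the report could take this to mean that no such data were collected under C.

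**Working it through.** The plan states no figure to reproduce. The check crosses the sequences with the schedule and then counts what is missing.

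**1. Period 4 treatment by sequence** (SAP Section 3; fourth letter of each sequence)

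| Sequence | Period 4 treatment | Hour 168 belongs under | Covered by the notes? |
|---|---|---|---|
| ABCD | D | D | yes |
| ABDC | C | C | no |
| BACD | D | D | yes |
| BADC | C | C | no |

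Two of four sequences end on C. No sequence ends on A or B, so an Hour 168 row is correctly empty for those two.

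**2. Is the omission explained elsewhere in the SAP?** Section 7.5 says that "Postdose recheck values and ET results will not be used for calculation of descriptive statistics", and Section 7.6 repeats the rule. It removes early-termination measurements. It does not remove the Period 4 Day 8 assessment of a subject who completes the study, which is a scheduled time point. The rule therefore gives no reason to drop Treatment C.

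**3. Comparison with the laboratory shells.** The laboratory schedule is not identical, because it has an end-of-period test in every period. The shift shell (Table 14.3.5.2) nevertheless gives both C and D a Day 7/8 row, with a footnote that assigns Day 7 to Period 3 and Day 8 to Period 4. In that shell the SAP recognises that either treatment can fall in Period 4.

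**4. Table cells left empty if the notes are followed literally.** The inputs are the parameters named for summary in SAP Sections 7.5 and 7.6, and the six statistics in the shells (n, mean, SD, minimum, median, maximum), each for the value and for the change from baseline.

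- Vital signs: systolic pressure, diastolic pressure, pulse, respiration: 4 × 6 × 2 = 48
- ECG: heart rate, PR, QRS, QT, QTcF: 5 × 6 × 2 = 60
- Total in the Treatment C columns: 48 + 60 = 108

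Temperature is not counted, because Section 7.5 does not name it for summary.

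**5. Share of completers left out of the Hour 168 summaries**

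Share = completers in (ABDC + BADC) / all completers

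With equal sequence sizes and no unequal dropout this is 50%. The sample size is redacted, so the following cases are assumptions that only show the sensitivity. Each takes equal allocation and two dropouts, both on the same side:

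| Assumed N | Both lost from C-last | Both lost from D-last |
|---|---|---|
| 12 | 4/10 = 40% | 6/10 = 60% |
| 24 | 10/22 = 45% | 12/22 = 55% |

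**The case against.** The strongest reply is that the governing text is already correct. Sections 7.5 and 7.6 schedule Hour 168 by period and ask for statistics by treatment. Section 10 warns that the shells show general layout, may change and may not reflect every aspect of the study. In both shells treatments are columns and time points are rows, so an added Hour 168 row would cross all four columns. A program that summarises by treatment would then fill C without being told to. On this view the data are lost only if someone deliberately suppresses C.

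Part of this stands: the loss is conditional on the notes being followed as written, and the programs are not visible. But the notes are specific instructions about content, given twice, and they attribute the extra time point to one treatment. Section 10 allows for unforeseen circumstances, and the sequences were fixed in the protocol from the start.

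A second reply concerns weight, and it largely stands. No inferential safety analysis is planned. Hours 2 and 72 are summarised for all four treatments. Every value is kept in the by-subject listings, and for the ECG, "QTcF values that are > 450 msec and increase from baseline > 30 msec will be flagged in the data listing". The protocol synopsis is also softer than protocol Section 14.3.2: it says only that summary statistics for ECGs and vital signs may be provided where clinically appropriate. That weakens the protocol's support for the requirement, but the SAP's own rule remains. Finally, the cell count measures the extent of the gap in the tables, not any effect on a conclusion, and the dropout cases are illustrations, not bounds.

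**Conclusion.** The concern holds and is minor. The notes to Tables 14.3.5.7 and 14.3.5.8 contradict the SAP's own schedule and summary rule, and nothing elsewhere in the documents corrects them. That the notes are wrong for two of the four sequences follows from the documents alone. That the gap reaches the report depends on the notes being programmed literally. That about half of completers are affected depends on roughly equal sequence sizes and similar dropout. The consequence is confined to the Hour 168 row of two descriptive safety tables. The PK comparisons and the listings are unaffected.

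**What to change.** Reword both programmer notes, for example: *Treatments C and D have an additional time point, Postdose Hour 168 (Period 4 only: D for ABCD and BACD, C for ABDC and BADC).*

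Add a matching table footnote, because n at Hour 168 in each column will count only subjects who received that treatment in Period 4 and had the scheduled Day 8 assessment. The C and D figures at that row therefore come from different subjects. Early-termination results stay excluded, as Sections 7.5 and 7.6 already provide.

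The cost is the wording of two notes and a footnote. No new data are needed and the listings do not change.

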## **11. LISTING SHELLS**

The following listing shells provide a framework for the display of data from this study. The shells may change due to unforeseen circumstances. These shells may not be reflective of every aspect of this study, but are intended to show the general layout of the listings that will be presented and included in the final CSR. These listings will be generated from the Celerion SDTM Tabulation Model 1.4 mapped in accordance with SDTM Implementation Guide 3.2. All listings will be presented in Courier New size font 9.

Appendix 16.1.10.1 Clinical Laboratory Reference Ranges

Laboratory Group	Test Name	Sex	Age Category	Normal Range	Unit
Serum Chemistry	Test Name	XXXXXX	XX	XX - XX	units
	Test Name	XXXXXX	XX	XX - XX	units
	Test Name	XXXXXX	XX	XX - XX	units
	Test Name	XXXXXX	XX	XX - XX	units
	Test Name	XXXXXX	XX	XX - XX	units
	Test Name	XXXXXX	XX	XX - XX	units
Hematology	Test Name	XXXXXX	XX	XX - XX	units
	Test Name	XXXXXX	XX	XX - XX	units
	Test Name	XXXXXX	XX	XX - XX	units
	Test Name	XXXXXX	XX	XX - XX	units
	Test Name	XXXXXX	XX	XX - XX	units

<Programmer note: Sort alphabetically by lab test name within each lab group.>

<similar for remaining Laboratory Groups and Test Names>

Program: /CAXXXX/sas\_prg/stsas/lis\_PROGRAMNAME.sas DDMMYYYY HH:MM

Appendix 16.2.1 Subject Discontinuation (Safety Population)

Subject Number	Treatment Sequence	Study Period	Date	Completed Study?	Primary Discontinuation Reason
XXX-XXX	ABCD	Post	DDMMYYYY	YES	
XXX-XXX	ABCD	Post	DDMMYYYY	YES	
XXX-XXX	ABCD	Post	DDMMYYYY	YES	
XXX-XXX	ABCD	Post	DDMMYYYY	YES	
XXX-XXX	ABCD	Post	DDMMYYYY	NO	Adverse Event
XXX-XXX	ABCD	Post	DDMMYYYY	YES	
XXX-XXX	ABCD	Post	DDMMYYYY	YES	
XXX-XXX	ABCD	Post	DDMMYYYY	YES	

Note: Treatment A: 160 mg LOXO-292 (2 x 80 mg capsules) at Hour 0 on Day 1 administered under fasting conditions.  
Treatment B: 160 mg LOXO-292 (2 x 80 mg capsules) at Hour 0 on Day 1 administered 30 minutes after the start of a high fat breakfast.  
Treatment C: Multiple daily doses of 40 mg omeprazole (1 x 40 mg capsule) from Day 1 to Day 7 with 160 mg LOXO-292 (2 x 80 mg capsules) coadministered at Hour 0 on Day 1 under fasting conditions.  
Treatment D: Multiple daily doses of 40 mg omeprazole (1 x 40 mg capsule) from Day 1 to Day 7 with 160 mg LOXO-292 (2 x 80 mg capsules) coadministered at Hour 0 on Day 1, 30 minutes after the start of a high fat breakfast.  
Prior to Treatment C or D at Period 3, subjects were administered with multiple daily doses of 40 mg omeprazole (1 x 40 mg capsule) from Day -4 to Day -1 of Period 3.

Program: /CAXXXX/sas\_prg/stsas/lis\_PROGRAMNAME.sas DDMMYYYY HH:MM

Appendix 16.2.4.1 Demographics (Safety Population)

Subject Number	Date of Birth	Age* (yr)	Sex	Race	Ethnicity	Height (cm)	Weight (kg)	Body Mass Index (kg/m^2)	Informed Consent Date	Informed Consent Version Date
XXX-XXX	DDMMYYYY	XX	AAAAAA	AAAAAAA	AAAAAAAAA	XXX	XX.XX	XX.XX	DDMMYYYY	DDMMYYYY
XXX-XXX	DDMMYYYY	XX	AAAAAA	AAAAAAA	AAAAAAAAA	XXX	XX.XX	XX.XX	DDMMYYYY	DDMMYYYY
XXX-XXX	DDMMYYYY	XX	AAAAAA	AAAAAAA	AAAAAAAAA	XXX	XX.XX	XX.XX	DDMMYYYY	DDMMYYYY
XXX-XXX	DDMMYYYY	XX	AAAAAA	AAAAAAA	AAAAAAAAA	XXX	XX.XX	XX.XX	DDMMYYYY	DDMMYYYY
XXX-XXX	DDMMYYYY	XX	AAAAAA	AAAAAAA	AAAAAAAAA	XXX	XX.XX	XX.XX	DDMMYYYY	DDMMYYYY
XXX-XXX	DDMMYYYY	XX	AAAAAA	AAAAAAA	AAAAAAAAA	XXX	XX.XX	XX.XX	DDMMYYYY	DDMMYYYY
XXX-XXX	DDMMYYYY	XX	AAAAAA	AAAAAAA	AAAAAAAAA	XXX	XX.XX	XX.XX	DDMMYYYY	DDMMYYYY

Note: \* Age is calculated from the date of first dosing.

Program: /CAXXXX/sas\_prg/stsas/lis\_PROGRAMNAME.sas DDMMYYYY HH:MM

Appendix 16.2.4.2 Updated Informed Consent (Safety Population)

Subject Number	Date Subject Signed Informed Re-Consent	Informed Re-Consent Version Date	Reason for Re-Consent
XXX-XXX	DDMMYYYY	DDMMYYYY	XXXXXXXXXXXX
XXX-XXX	DDMMYYYY	DDMMYYYY	XXXXXXXXXXXX
XXX-XXX	DDMMYYYY	DDMMYYYY	XXXXXXXXXXXX
XXX-XXX	DDMMYYYY	DDMMYYYY	XXXXXXXXXXXX
XXX-XXX	DDMMYYYY	DDMMYYYY	XXXXXXXXXXXX
XXX-XXX	DDMMYYYY	DDMMYYYY	XXXXXXXXXXXX
XXX-XXX	DDMMYYYY	DDMMYYYY	XXXXXXXXXXXX

Program: /CAXXXX/sas\_prg/stsas/lis\_PROGRAMNAME.sas DDMMYYYY HH:MM

Appendix 16.2.4.3 Physical Examination (Safety Population)

Subject Number	Treatment Sequence	Period	Day	Hour	Date	Body System	Answer or Result	Comment
XXX-XXX	ABCD	Screen			DDMMYYYY	Was PE performed? General HEENT < >	Yes Normal Normal < >	
		1	-1	Check-in	DDMMYYYY	Was PE performed? HEENT < >	Yes Unchanged < >	

Note: Treatment A: <description>  
Treatment B: <description>  
Treatment C: <description>  
Treatment D: <description>

Prior to Treatment C or D at Period 3, subjects were administered with multiple daily doses of 40 mg omeprazole (1 x 40 mg capsule) from Day -4 to Day -1 of Period 3.

Program: /CAXXXX/sas\_prg/stsas/lis\_PROGRAMNAME.sas DDMMYYYY HH:MM

Appendix 16.2.4.4 Medical and Surgical History (Safety Population)

Subject Number	Any History?	Study Period	Category	Body system	Date		Ongoing?	Condition or Events
					Start	End		
XXX-XXX	XXX	Screen	Medical Surgical	XXXXXXXXXXXX	DDMMYYYY DDMMYYYY	DDMMYYYY DDMMYYYY	YES	XXXXXX XXXXXX XXXXXXXX
XXX-XXX	XXX	Screen	Medical	XXXXXXXXXXXX	DDMMYYYY	DDMMYYYY	NO	

Program: /CAXXXX/sas\_prg/stsas/lis\_PROGRAMNAME.sas DDMMYYYY HH:MM

Appendix 16.2.4.5 Nicotine Use (Safety Population)

Subject Number	Study Period	Substance	Description of Use	Start Date	End Date
XXX-XXX	Screen	XXXXXXXX XXX	XXXXX XXXXXX XXXXX	DDMMYYYY	DDMMYYYY

Program: /CAXXXX/sas\_prg/stsas/lis\_PROGRAMNAME.sas DDMMYYYY HH:MM

Appendix 16.2.5.1.1 Inclusion Criteria

1. Healthy, adult, male or female (of non-childbearing potential only), 18-55 years of age, inclusive, at screening.
2. < >
3. < >
4. < >
5. < >

Program: /CAXXXX/sas\_prg/stsas/lis\_PROGRAMNAME.sas DDMMYYYY HH:MM

Appendix 16.2.5.1.2 Exclusion Criteria

1. Is mentally or legally incapacitated or has significant emotional problems at the time of the screening visit or expected during the conduct of the study.
2. < >
3. < >
4. < >
5. < >
6. < >
7. < >

Program: /CAXXXX/sas\_prg/stsas/lis\_PROGRAMNAME.sas DDMMYYYY HH:MM

Page 1 of 1

Appendix 16.2.5.2 Subject Eligibility (Safety Population)

Subject Number	Study Period	Did subject meet all eligibility criteria?	Specify
XXX-XXX	Screen	YES	
XXX-XXX	Screen	NO	<this column is only presented if data is present>

Program: /CAXXXX/sas\_prg/stsas/lis\_PROGRAMNAME.sas DDMMYYYY HH:MM

Appendix 16.2.5.3.1 Check-in Criteria

1. Did the Subject report any study restriction violations since the last study visit?
2. IF YES TO ANY QUESTION, WAS SUBJECT APPROVED FOR STUDY?

Program: /CAXXXX/sas\_prg/stsas/lis\_PROGRAMNAME.sas DDMMYYYY HH:MM

Page 1 of X

Appendix 16.2.5.3.2 Check-in Responses (Safety Population)

Subject Number	Treatment Sequence	Study Period	Day	Hour	Date	Time	Check-in Criteria		Specify
							X	X	
XXX-XXX	ABCD	1	X	Check-in	DDMMYYYY	hh:mm:ss	YES	YES	<this column prints only if data is present>

Note: Treatment A: <description>  
Treatment B: <description>  
Treatment C: <description>  
Treatment D: <description>

Prior to Treatment C or D at Period 3, subjects were administered with multiple daily doses of 40 mg omeprazole (1 x 40 mg capsule) from Day -4 to Day -1 of Period 3.

Program: /CAXXXX/sas\_prg/stsas/lis\_PROGRAMNAME.sas DDMMYYYY HH:MM

